6.4.10.3. Medication and Medical History

A complete medical history will be taken during the screening visit (for De Novo subjects only) and will include evaluation of past and present cardiovascular, respiratory, GI, renal, hepatic, neurological, endocrine, lymphatic, hematologic, immunologic, dermatologic, psychiatric, genitourinary, substance abuse, surgical history, or any other diseases or disorders. Medical conditions will be recorded for 2 years prior to screening visit, along with the date of diagnosis, and any other relevant medical history that has an impact to the subject.

Medical events or conditions that arise or worsen in severity or frequency after the signing of the informed consent will be recorded as an AE.

All medications used during the 60 days prior to screening will be recorded in the source records. The only exception is drugs that were used to treat previous orthostatic hypotension; these will be recorded since the time of primary diagnosis.

6.4.10.4. Physical Examination

A full physical examination at the screening visit will be performed by an appropriately qualified individual (e.g., physician, nurse practitioner, physician's assistant, or equivalent, under the supervision of a physician) and will include examination of the following: general appearance; skin; head, ears, eyes, nose, and throat; neck; cardiovascular system; respiratory system; abdomen/ GI system; extremities; lymphatic system [lymph nodes]; and nervous system).

Subsequent physical examinations, after the screening visit, per discretion of the Investigator, can be abbreviated and symptomatic, largely focused on evaluation of AEs, if any, and any abnormalities identified on the screening visit examination.

6.4.10.5. Neurological Examination

Any abnormalities identified at the screening visit will be recorded as neurological medical history. Any abnormalities or symptoms reported during treatment that arise or worsen in severity or frequency will be reported as AEs.

The PI should perform a neurological exam in clinic or via telemedicine platform for remote visits (assisted as necessary by the home health nurse) as required to assess the subject's current condition and include the following exams per the PI's medical discretion.

The examination will assess the following:

- Cranial nerves (cranial nerves II-XII, excluding funduscopic examination)
- Motor system (tone, strength, and abnormal movements)
- Sensory system (light touch, pinprick, joint position, and vibration)
- Reflexes (deep tendon reflexes and plantar responses)
- Coordination (upper and lower extremities)
- Gait (base and tandem gait)
- Station (posture and stability)

6.4.10.6. Height and Weight

Height (in cm) and weight (in kg) will be recorded as outlined in the Schedule of Study Procedures ([Table 1](#)). Reasonable efforts will be taken to ensure the measurements for weight occur at approximately the same time each visit using the same scale and with similar clothing.

6.4.10.7. Vital Signs

The HR, SBP and DBP, RR, and body temperature will be recorded according to the Schedule of Study Procedures ([Table 1](#)). The vital sign measurements (BP and HR) should be performed after the subject has rested sufficiently as determined by the appropriate staff.

Subject position, measurement device, and arm (left vs. right) should be kept consistent throughout the study. Blood pressure will be measured using a calibrated manual or automatic BP device.

Heart rate will be recorded by palpation of the radial pulse over at least a 30-second period or by the automated BP device.

The BP and HR collected at 10 minutes supine and seated from the orthostatic standing test can be used for safety vital sign assessment.

Body temperature will be measured and reported in degrees Celsius. The method used to collect temperature can be either oral or tympanic but should be consistent throughout the subject's participation.

Any vital sign outside the normal range may be repeated at the discretion of the Investigator. Collection of additional vital sign measurements for routine safety monitoring at additional time points or study days may be performed at the discretion of the Investigator, or upon request by the sponsor.

6.4.10.8. Electrocardiograms

The 12-lead ECGs will be recorded in triplicate and separated by at least 1 minute for each replicate, according to the Schedule of Study Procedures ([Table 1](#)), after the subject has been resting at least 5 minutes in the seated or supine position before the first reading. The total time to conduct ECGs ideally would not exceed 15 minutes. Actual time of the assessment must be recorded for each iteration. The corrected QT interval using the Fridericia's formula (QTcF) will be used. The ECGs should be reviewed on the visit day to allow for any appropriate action, if required.

6.4.10.9. 24-hour Ambulatory Blood Pressure Monitoring

Ambulatory blood pressure monitoring (ABPM) equipment will be provided to the subject during the screening visit for De Novo Group subjects, and on V1 for 0169 Completers Group subjects. Beginning approximately 72 to 24-hours before a subject returns to the scheduled clinic visits that require the procedure, subjects will put on the 24-hour blood pressure monitoring equipment and initiate the recording. Once the 24-hour session is complete, subjects will remove and return the equipment to the research center during the next visit. During each 24-hour session, the BP monitoring device will be programmed to automatically measure BP every 2 hours beginning at the top of the hour. During each 24-hour session, subjects will log their posture at the time of each BP measurement in the provided ABPM Position Diary ([Appendix 4](#)). More details regarding the ambulatory monitoring will be provided in a separate manual. ABPM will be performed as specified in the Schedule of Study Procedures ([Table 1](#)).

6.4.10.10. Laboratory Tests

Laboratory tests will be performed as specified in the Schedule of Study Procedures ([Table 1](#)). Additional and repeat laboratory safety testing for the evaluation of abnormal results and/or AEs during the study may be performed at the discretion of the Investigator or upon request of the sponsor.

Detailed instructions and collection kits for sample collection, handling, and shipping will be provided in the laboratory manual.

6.4.10.10.1. Hematology

Hematology samples will be analyzed for the following: hematocrit and hemoglobin; red blood cell count; mean corpuscular volume; mean corpuscular hemoglobin; white blood cell count, including differential count (percent and absolute) of neutrophils, eosinophils, basophils, monocytes, lymphocytes; platelet count and HgbA1C (if applicable).

6.4.10.10.2. Chemistry

Chemistry samples will be analyzed for the following: sodium, potassium, calcium, chloride, bicarbonate, glucose, blood urea nitrogen, creatinine, eGFR, total protein, albumin, alkaline phosphatase, ALT, AST, bilirubin, lactate dehydrogenase, and creatine phosphokinase.

6.4.10.10.3. Urinalysis

Urinalysis includes determination of specific gravity; presence of blood, protein, and leukocytes; and microscopic examination of sediment, if clinically indicated.

6.4.10.11. Dosing Diary Dispensation and/or Collection

On a daily basis, the subjects will record the time of study medication administration in the diary provided on V1. Dosing diary with completion instructions, including study medication dosing details, will be provided to each subject. Subjects will be instructed to record daily dosing through the end of the treatment period ([Appendix 5](#)). Diary completion will be monitored for completeness at each return study visit after the diary is dispensed. Subjects will be counseled on missed study medication doses and missed diary entries. Compliance with the dosing regimen will be assessed by reconciliation of used and unused study medication.

6.4.10.12. Unscheduled Visit

All sites are allowed at Investigator discretion to conduct either in clinic or remote unscheduled visit(s) for subject safety or unexpected subject medical needs outside of the regular visit schedule. In this case, unscheduled visits are not considered protocol deviations and the Investigator is not required to obtain pre-approval from the Sponsor. Data collected during these visits may include any protocol-specified assessments which will be captured in the clinical database.

6.5. Concomitant Medications

For the De Novo Group, subjects should not have changed dose, frequency, or type of prescribed medication for orthostatic hypotension within 7 days prior to V1/D1.

Concomitant use of antihypertensive medication for the treatment of essential hypertension is not allowed.

Subjects can continue on a stable dosing regimen of fludrocortisone if the regimen was initiated at least 7 days prior to V1/D1.

Cannabinoids usage for medical reasons is permissible at a stable dosing regimen established at least 7 days prior to V1/D1 in countries where cannabinoids are permissible.

Stable dosing regimen is defined as the same dosage and frequency on any given day.

Subjects who are smokers will be recommended to either stop smoking (cigarettes or cannabinoids in countries where cannabinoids are permissible) at least 7 days before first dose or maintain a constant smoking habit during the entire course of the study.

6.5.1. Impact of Other Medications on TD-9855

Preliminary results from the clinical drug-drug interaction study suggest that concomitant administration of itraconazole (CYP3A4 inhibitor) resulted in minimal impact on the exposure of TD-9855 while concomitant administration of fluvoxamine (CYP1A2 inhibitor) resulted in significant increase in TD-9855 exposure. Additionally, TD-9855 exposure was lower in subjects who are smokers as compared to nonsmokers. Accordingly, it is expected that TD-9855 metabolism is primarily driven by the CYP1A2 enzyme. Restrictions on the concomitant use of strong CYP1A2 inhibitors and inducers are described in Section 6.7.

6.5.2. Impact of TD-9855 on Other Medications

In vitro evaluation indicates that clinical drug-drug interactions due to CYP450 metabolism or transporters with TD-9855 as the perpetrator are not anticipated in humans. Thus, no clinical studies have been conducted and no impact on exposure of concomitant medications is expected.

6.6. Rescue Medications

Usage of any rescue medications is discouraged during the course of the study. However, under exceptional circumstances, based on the discretion of the Investigator and to ensure subject's safety, midodrine is permitted as follows:

- A maximum of 10mg (increments of 2.5mg are available) may be administered, one day per week
- Cannot be used on the assessment days

Dosing instructions will be provided by the Investigator as dosing for this medication will differ between subjects. Subjects will record their use of midodrine in the Midodrine Rescue Medication Diary. Midodrine use will be captured in the database. Refer to [Appendix 6](#).

6.7. Prohibitions and Restrictions

The following are prohibited or restricted during study participation as specified:

- For the De Novo Group, subjects must stop the concomitant use of strong CYP1A2 inhibitors and inducers 7 days or 5 half-lives, whichever is longer, prior to V1. This restriction applies to concomitant medications, herbal supplements (e.g., St. John's Wort), and ordinary dietary intake. Refer to [Appendix 7](#) for a list of prohibited medications.
- Prescribed medications for OH other than fludrocortisone are prohibited
- Alpha blockers are prohibited (e.g., Prazosin, Terazosin, Doxazosin, Silodosin, Alfuzosin, Tamsulosin)
- Norepinephrine reuptake inhibitors (NRIs) and serotonin and norepinephrine reuptake inhibitors (SNRIs) are prohibited
 - NRIs (e.g. atomoxetine and reboxetine) and SNRIs (e.g. duloxetine, milnacipran, levomilnacipran, venlafaxine, desvenlafaxine)

- Psychostimulants (e.g. amphetamine, dextroamphetamine, methylphenidate, pemoline) are prohibited
- Subjects will be requested to refrain from making any significant dietary changes throughout the duration of the study. During their scheduled visits, subjects should be reminded to maintain an adequate fluid intake.

6.8. Discontinuation

6.8.1. Dose Stopping Rules

Any subject meeting 1 or more of the following stopping criteria will be required to immediately discontinue dosing with study medication and subsequently subject will be discontinued from participation in the study:

- A determination from the Investigator that further administration of the study medication may pose a safety concern to the subject
- Sustained (at least 4 hours) SBP \geq 180 mmHg or diastolic BP (DBP) \geq 110 mmHg after 3 min of standing or after 5 min in the sitting position, or a sustained (at least 4 hours) SBP \geq 180 mmHg or DBP \geq 110 mmHg measured in the supine state (head/torso elevated at approximately 30° from horizontal position).
- Intolerable AE as determined by the Investigator
- Subject becomes pregnant

6.8.2. Subject Discontinuation

Any subject (or his or her legally authorized representative) may withdraw their consent to participate in the study at any time without prejudice. The Investigator must withdraw from the study any subject who requests to be withdrawn. A subject's participation in the study may be discontinued at any time at the discretion of the Investigator and in accordance with his or her clinical judgment. When possible, the tests and evaluations listed for the termination visit should be completed. If a subject withdraws before completing the study, the reason for withdrawal is to be documented on the CRF.

The sponsor will be notified of all subject withdrawals.

Reasons for which the Investigator may withdraw a subject from the study or a subject may choose to terminate participation before completion of the study include, but are not limited to, the following:

- Adverse Event
- Physician Decision
- Pregnancy
- Protocol Violation
- Withdrawal by Subject
- Other

The subject may also discontinue from the study if the study is discontinued by the Sponsor

Subjects who discontinue study medication early because of an adverse reaction should be encouraged to continue their participation in the follow-up safety assessments. If a subject fails to return for scheduled visits, a documented effort must be made to determine the reason.

6.8.3. Subject Replacement

Subjects will not be replaced.

6.8.4. Study Discontinuation

The sponsor reserves the right to discontinue this study at any time for any reason.

Periodic review of unblinded safety data by an external IDMC (Section 8.8) may lead to the board's recommendation of pausing dosing or terminating the study. In the event of premature study termination, best efforts to guarantee appropriate safety follow-up of subjects who have already been enrolled will be made and institutional review boards (IRBs) and the regulatory authorities will be informed.

6.9. Pregnancy

TD-9855 has been shown to be non-genotoxic in a standard battery of genotoxicity assays (in vitro Ames and chromosomal aberration assays and in vivo micronucleus assay in rat). TD-9855 demonstrated effects on neonatal mortality and decreased rates of pup growth in the pre- and postnatal study in rats. Based on the NOAEL in reproductive-toxicology studies in preclinical species, there exists a greater than 100x margin between exposure in preclinical species at NOAEL vs. exposure in male and female subjects at 4 weeks post stopping administration of 10-mg TD-9855 dose. Thus, application of pregnancy prevention measures for 30 days post last dose of TD-9855 is sufficient to address the risk of substantial drug exposure in semen or maternal circulation.

To confirm the absence of pregnancy in female subjects of childbearing potential, urine bHCG testing will be performed during specified visits, as listed in the Schedule of Study Procedures (Table 1). If the urine bHCG test is positive, a serum bHCG test must be performed. The pregnancy test must be confirmed negative for a subject to be eligible for this study unless the PI deems the test is falsely positive.

If a subject becomes pregnant while taking TD-9855, or during the 30 days after the last dose of treatment, the pregnancy must be reported to the sponsor's medical monitor (or designee) immediately (within 24-hours) by following the procedures for SAE reporting as outlined in Section 7.4.3. Study drug must be discontinued for any pregnant subject still on study drug treatment. Follow-up information regarding the outcome of the pregnancy and any postnatal sequelae in the infant will be required.

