Safety will be periodically reviewed by an Independent Data Monitoring Committee (IDMC).

Subjects will be requested to refrain from making any significant dietary changes throughout the duration of the study. During their scheduled visits, subjects should be reminded to maintain an adequate fluid intake.

Subjects completing the 6-week double-blind treatment period will be eligible to continue into the OL, long-term safety study (Study 0171). Those subjects who do not complete the 6-week double-blind treatment period or who choose not to continue into Study 0171 will complete the Early Termination Visit (V9) or Follow-up visit (V10), respectively. The Follow-Up Visit must be completed 2 weeks from the date of the last dose.

PROTOCOL SYNOPSIS (CONTINUED)

Duration of Study Participation: Up to 24 weeks for subjects coming from Study 0169 and up to 28 weeks for de novo subjects.

Number of Subjects: The total number of subjects participating in this study will be approximately 258. After the 16-week OL phase, at least 154 subjects are expected to be randomized to either the TD-9855 or the PBO group, stratified by the subject's background disease type (MSA, PD, or PAF), assuming 60% are eligible for randomization at the end of the OL phase.

For the De Novo Group, the goal is to enroll at least 40% of MSA subjects.

All completers from study 0169 will be eligible to participate in study 0170. Assuming 10% early discontinuation, approximately 170 subjects are anticipated to be eligible for the 0169 Completers Group.

Study Population:

This study will enroll adult subjects with confirmed symptomatic nOH due to MSA, PD or PAF and who meet the inclusion and exclusion criteria defined below. Eligible subjects may be de novo or completers from Study 0169.

Inclusion Criteria (For 0169 Completers Group):

101. Completion of 4 weeks of double-blind treatment in Study 0169 (V6) and, in the opinion of the Investigator, could benefit from continued treatment with TD-9855. No minimum score of OHSA#1 is required to enter V1 of Study 0170.
102. The subject has a minimum of 80% study medication compliance in Study 0169.
103. The subject must be able to understand the nature of the study and must provide written informed consent prior to the conduct of any study procedures (including an understanding that entry to Study 0170 may result in changes occurring in the subject's current therapeutic regimen).

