104. The subject must be willing to continue on treatment regardless of the possibility of randomization to either TD-9855 or PBO during the randomized withdrawal phase and must continue to meet the inclusion criteria for the preceding study (Study 0169) with the exception that tilt-table test, ESC review and approval of eligibility are not required for entry into Study 0170.

Inclusion Criteria (For De Novo Group):

1. Subject is male or female and at least 30 years old.
2. If subject is female, the subject must be non-pregnant and non-lactating. A woman of childbearing potential must have a documented negative pregnancy test at screening.

NOTE: A woman is considered to be of childbearing potential unless she is postmenopausal (amenorrheic for at least 2 years) or documented to be surgically sterile (bilateral tubal ligation or total hysterectomy). A female subject may be admitted to the study on the basis of a negative urine pregnancy test. If the urine beta human chorionic gonadotropin (bHCG) test is positive, a serum bHCG test must be

PROTOCOL SYNOPSIS (CONTINUED)

performed. The pregnancy test must be confirmed negative for a subject to be eligible for this study.

3. During the study and for 30 days after receiving the last dose of the study drug, females of childbearing potential or males capable of fathering children must agree to use highly effective birth control measures (failure rate <1% when used consistently and correctly) or agree to abstain from sexual intercourse (Refer to Section 4.3).
4. Subject must meet the diagnostic criteria of nOH, as demonstrated by a sustained reduction in BP of ≥ 20 mmHg (systolic) or ≥ 10 mmHg (diastolic) within 3 min of being tilted up $\geq 60^\circ$ from a supine position as determined by a tilt-table test.
5. Subject must score at least a 4 on the OHSA#1 at V1.
6. For subjects with PD only: Subject has a diagnosis of PD according to the United Kingdom Parkinson's Disease Society (UKPDS) Brain Bank Criteria (1992).
7. For subjects with MSA only: Subject has a diagnosis of possible or probable MSA of the Parkinsonian subtype (MSA-P) or cerebellar subtype (MSA-C) according to The Gilman Criteria (2008).
8. For subjects with PAF only: Subject has documented impaired autonomic reflexes, including the Valsalva maneuver performed within 24 months from the date of randomization.
9. Subject has plasma NE levels ≥ 100 pg/mL after being in seated position for 30 minutes.

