4.1. Inclusion Criteria

A subject who meets the following applicable criteria will be eligible for study enrollment:

Inclusion Criteria (For 0169 Completers Group):

101. Completion of 4 weeks of double-blind treatment in Study 0169 (V6) and, in the opinion of the Investigator, could benefit from continued treatment with TD-9855. No minimum score of OHSA#1 is required to enter V1 of Study 0170.
102. The subject has a minimum of 80% study medication compliance in Study 0169.
103. The subject must be able to understand the nature of the study and must provide written informed consent prior to the conduct of any study procedures (including an understanding that entry to Study 0170 may result in changes occurring in the subject's current therapeutic regimen).
104. The subject must be willing to continue on treatment regardless of the possibility of randomization to either TD-9855 or PBO during the randomized withdrawal phase and must continue to meet the inclusion criteria for the preceding study (Study 0169) with the exception that tilt-table test, ESC review and approval of eligibility are not required for entry into Study 0170.

Inclusion Criteria (For De Novo Group):

1. Subject is male or female and at least 30 years old.
2. If subject is female, the subject must be non-pregnant and non-lactating. A woman of childbearing potential must have a documented negative pregnancy test at screening.

NOTE: A woman is considered to be of childbearing potential unless she is postmenopausal (amenorrhic for at least 2 years) or documented to be surgically sterile (bilateral tubal ligation or total hysterectomy). A female subject may be admitted to the study on the basis of a negative urine pregnancy test. If the urine beta human chorionic gonadotropin (bHCG) test is positive, a serum bHCG test must be performed. The pregnancy test must be confirmed negative for a subject to be eligible for this study.

3. During the study and for 30 days after receiving the last dose of the study drug, females of childbearing potential or males capable of fathering children must agree to use highly effective birth control measures (failure rate <1% when used consistently and correctly) or agree to abstain from sexual intercourse. (Refer to Section 4.3).

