4.3. Pregnancy and Contraception

4.3.1. Females of Childbearing Potential

Females of childbearing potential must have documentation of a negative pregnancy test at screening and prior to dosing.

Females are considered to be not of childbearing potential if they have had a total hysterectomy and/or bilateral tubal ligation or hysteroscopic sterilization (documentation for surgeries must be provided before randomization) or are in a postmenopausal state (i.e., females who have had cessation of prior occurring menses for ≥ 24 months without alternative causes or females with premature ovarian failure).

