6.4.1. Demographic and Baseline Assessments

Demographic information to be collected will include: year of birth, sex, race, and ethnicity.

For De Novo Group subjects, inclusion and exclusion criteria will be assessed at screening and on Day 1 prior to OL treatment. Subjects will only be eligible for enrollment into the study if they meet all the applicable inclusion and none of the applicable exclusion criteria. Each subject will be asked to provide relevant medical history (including medication history; see Section 6.4.10.3).

For 0169 Completers Group subjects, the data would be confirmed with information captured in Study 0169.

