4. STUDY DESIGN

4.1. Overview

This is a Phase 3, multi-center, randomized withdrawal study to evaluate the sustained benefit in efficacy and safety of TD-9855 in subjects with primary autonomic failures (MSA, PD, or PAF) and snOH. The following is a summary of the study design. For a full description, refer to the study protocol.

Eligible subjects are either (i) completers of Study 0169 (0169 Completers Group), or (ii) snOH subjects meeting all applicable study inclusion criteria and none of the applicable exclusion criteria (De Novo Group). The principal eligibility criteria for the 0169 Completers Group are as follows:

- Subject has completed 4 weeks of double-blind treatment in Study 0169 (V6) and, in the opinion of the investigator, could benefit from continued treatment with amprelosetine. No minimum score of OHSAs#1 is required to enter V1 of Study 0170.
- Subject had $\geq 80\%$ study medication compliance in Study 0169

For the De Novo Group, the eligibility criteria are the same as for Study 0169. The principal criteria are as follows:

- Subject is male or female and ≥ 30 years old
- Subject meets the diagnostic criteria of symptomatic nOH, as demonstrated by a sustained reduction in BP of ≥ 20 mm Hg (systolic) or ≥ 10 mm Hg (diastolic) within 3 min of being tilted up $\geq 60^\circ$ from a supine position as determined by a tilt-table test
- Subject must score ≥ 4 on the OHSAs#1 at V1
- For subjects with PD only: Subject has a diagnosis of PD according to the United Kingdom Parkinson's Disease Society (UKPDS) Brain Bank Criteria (1992)
- For subjects with MSA only: Subject has a diagnosis of possible or probable MSA of the Parkinsonian subtype (MSA-P) or cerebellar subtype (MSA-C) according to The Gilman Criteria (2008)
- For subjects with PAF only: Subject has documented impaired autonomic reflexes, including the Valsalva maneuver performed within 24 months from the date of enrollment
- Subject has plasma norepinephrine levels ≥ 100 pg/mL after being in a seated position for 30 minutes

For the complete lists, refer to the Study 0169 and Study 0170 protocols.

The study has 3 periods: (i) 16-week open-label treatment with TD-9855, (ii) 6-week randomized treatment with blinded TD-9855 or blinded placebo, and (iii) 2-week follow-up (only for patients who do not enroll in Study 0171).

Subjects entering from Study 0169 (0169 Completers Group)

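### Section 6.9 lets the PI set aside the confirmed-negative pregnancy test that every other eligibility passage requires without exception

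*Protocol*

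**What the plan says.** Section 6.9 of the protocol sets out pregnancy testing for women of childbearing potential. The sequence is urine first, then serum: "If the urine bHCG test is positive, a serum bHCG test must be performed". The next sentence makes a confirmed negative test a condition of eligibility but adds an exception: "unless the PI deems the test is falsely positive".

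The same rule appears elsewhere without that exception:

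- **Inclusion criterion 2 (De Novo Group), Synopsis and Section 4.1.** A negative test must be documented at screening, a positive urine test must be followed by serum, and "The pregnancy test must be confirmed negative for a subject to be eligible for this study".
- **Table 1, footnote o.** The same urine-then-serum sequence and the same closing sentence, not restricted to either enrollment group.
- **Section 4.3.1.** "Females of childbearing potential must have documentation of a negative pregnancy test at screening and prior to dosing". It is not restricted by group and does not mention serum testing.

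For enrollment as a whole, Section 6.4.1 states: "Subjects will only be eligible for enrollment into the study if they meet all the applicable inclusion and none of the applicable exclusion criteria".

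**The concern.** Two rules on one eligibility question cannot both be followed when a positive test has not been refuted. Section 6.9 would allow enrollment on the PI's opinion; criterion 2, footnote o and Section 4.3.1 would not.

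The rule protects the fetus. Section 6.9 itself reports effects on neonatal mortality and pup growth in rats and requires study drug to be stopped in any pregnant subject. Section 6.8.1 makes pregnancy a stopping rule. The exposure margin of more than 100-fold quoted in Section 6.9 refers to exposure four weeks after dosing stops. It supports the 30-day contraception period, not dosing during pregnancy.

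At stake are a possible exposure in pregnancy and, whether or not the woman is pregnant, an eligibility deviation at a site that believed it was following the protocol.

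**Working it through.** The plan gives no figure to reproduce. The check compares texts, with a small amount of arithmetic to bound the exposure.

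**1. The passages side by side**

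| Place | Applies to | Serum test after positive urine | Negative result required | PI exception |
|---|---|---|---|---|
| Criterion 2 (Synopsis, Section 4.1) | De Novo | Yes | Yes, confirmed | None |
| Table 1, footnote o | Not limited by group | Yes | Yes, confirmed | None |
| Section 4.3.1 | Not limited by group | Not mentioned | Yes, documented at screening and before dosing | None |
| Section 6.9 | Not limited by group | Yes | Yes, confirmed | Yes |

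The exception stands in one of the four places.

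**2. What the exception can do**

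Section 6.9 does not say whether the test the PI may discount is the urine or the serum test.

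- Urine positive, serum negative: the test is confirmed negative, the condition is met, and the exception adds nothing.
- Urine positive, serum not negative or not available: there is no confirmed negative. Only here does the exception change the outcome. Section 6.9 asks for no repeat test, criteria or medical monitor agreement.

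**3. Which subjects**

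De Novo women fall under criterion 2, footnote o and Section 4.3.1. Completers of Study 0169 fall under footnote o and Section 4.3.1. Criterion 104 also holds them to the Study 0169 inclusion criteria, apart from the tilt-table test and the steering committee's review and approval. The Study 0169 protocol is not among the documents, but SAP Section 4.1 says: "For the De Novo Group, the eligibility criteria are the same as for Study 0169".

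The Synopsis expects that "approximately 170 subjects are anticipated to be eligible for the 0169 Completers Group", out of approximately 258 subjects: 170 / 258 = 65.9%. For these subjects Day 1 is the only pregnancy test that this protocol schedules before dosing. De Novo women are tested at screening (Day -28 to -7) and again on Day 1. The 65.9% is a share of all subjects; the number of women of childbearing potential is not given.

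**4. Possible exposure**

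Dosing starts on Day 2, and on-treatment visit procedures follow that day's dose, so doses taken by Day d = d - 2 + 1 = d - 1. After Day 1, Table 1 next schedules a pregnancy test on Day 113.

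| Visit | Doses on the nominal day | With the +/- 3-day window | Pregnancy test scheduled |
|---|---|---|---|
| Day 15 | 14 | 11 to 17 | No |
| Day 29 | 28 | 25 to 31 | No |
| Day 57 | 56 | 53 to 59 | No |
| Day 85 | 84 | 81 to 87 | No |
| Day 113 | 112 | 109 to 115 | Yes |

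The worst case is 112 doses (16 weeks). It needs the pregnancy to go unnoticed at four visits, each with adverse event review, and the Day 29 continuation criterion to be met. If the pregnancy came to light at an earlier visit, the stopping rule would limit exposure to that row.

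**The case against.** The strongest reply is that Section 4 is the eligibility gate and Section 6.9 only describes procedures. The opening of Section 4 enrolls those who meet all applicable inclusion criteria, and Section 3.5.3 has the Investigator determine eligibility from the inclusion and exclusion criteria. Section 6.4.1 says the same, although its paragraph opens with the De Novo Group. A PI's opinion cannot supply the documented negative test in criterion 2. On that view the stricter rule already governs and Section 6.9 is loose drafting. This stands in part: the stricter rule is the better reading. But no text says which section prevails, and Section 6.9 is worded as an eligibility condition in its own right.

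A second reply is that the clause may mean only a urine positive that serum has already refuted. That reading is possible and harmless, but it makes the clause redundant. Nothing in the wording confines the clause to it.

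The limits on size are fair:

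- The completers' share does not measure the risk, and any pregnancy testing done within Study 0169 cannot be seen.
- The contraception-or-abstinence requirement (criterion 3, Section 4.3.2) lowers the chance of pregnancy.
- Section 6.9 also reports that the drug is non-genotoxic.
- The 112-dose figure needs several failures in a row.

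These keep the point small; they do not reconcile the texts.

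**Conclusion.** The concern holds, as a minor one. Section 6.9 contains an exception that criterion 2, footnote o and Section 4.3.1 do not allow. It is either redundant or an override with no evidence standard.

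Very few subjects are likely to be affected. De Novo entry is at age 30 or older, and the mean age in the open-label part of the earlier nOH study was 64 (Section 1.3). Harm arises only if the PI wrongly judges a true positive to be false; a De Novo pregnancy already detectable at screening would have to be misjudged twice. The worst case of 112 doses assumes daily dosing from Day 2 and no detection before Day 113. The application of criterion 2's rule to completers rests on the SAP's statement about Study 0169, but footnote o and Section 4.3.1 cover them in any case. The primary analysis, power and sample size are unaffected.

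**What to change.** Delete the nine words "unless the PI deems the test is falsely positive" from Section 6.9, so that its sentence matches criterion 2 and footnote o. This is one edit in the next amendment. No other passage needs changing, and the schedule, sample size and analyses stay as they are.

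The downside is that a rare woman with a truly false-positive serum test may be excluded. If the sponsor wants to keep discretion for that case, the alternative is to define it by objective evidence, such as repeat testing with medical monitor agreement, and to state it identically in criterion 2, footnote o, Section 4.3.1 and Section 6.9. That means more editing for very few subjects; deletion is simpler.
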